7.2 Rationale for the Study

This study is being conducted to evaluate the efficacy, safety and PK of ibrexafungerp in male and female subjects ≥ 18 years of age with documented severe fungal diseases for whom SOC antifungal treatment is not appropriate due to refractoriness, resistance, intolerance, relapse, toxicities, need for oral therapy or other reasons.

Eligible subjects must be selected based on study criteria and be approved for selection by the Sponsor or Sponsor designee.

Subjects must have a documented eligible fungal disease that has been refractory to, has relapsed after, or the subject has intolerance to or demonstrated toxicities resulting from an approved SOC antifungal treatment, or has an isolate resistant to, or that has a high MIC and is unlikely to respond to SOC antifungal treatment. Subjects are also eligible if, in the judgement of the Investigator, continued IV antifungal therapy is not feasible or desirable due to clinical or logistical circumstances or if other oral antifungal alternatives are not appropriate. Refractoriness, defined as persistent clinical, radiological or mycological evidence of fungal disease, and intolerance, including presence of, history of or anticipated toxicities (e.g. drug-to-drug interactions) associated with administration of SOC antifungal agents, will be determined by the Investigator.

The primary efficacy endpoint of the study is Global Response (composite assessment of clinical, radiological and mycological responses) as determined by a Data Review Committee (DRC). The primary endpoint will be determined at the TOC visit for VVC, CMC, CPA and ABPA and at the EOT visit for all other fungal diseases.^{7,8} Clinical response will be evaluated by the signs and symptoms of the infection and/or imaging scans, if applicable. Mycological response will be assessed by mycological testing (fungal culture, KOH and other fungal stains, T2 testing) and/or serological testing (including GMI, *Coccidioides* titers, and β -D-glucan levels, among others),⁹ if applicable. Recurrence will be assessed at the 25-Day FU visit (25 days after EOT) for subjects with VVC and at the 6-Week FU visit (42 days after EOT) for all other subjects as a secondary efficacy endpoint. Recurrence is defined as Global Response at EOT (TOC for VVC) but re-emergence of the baseline fungal disease (with the same fungal species and involving the same site) during the post treatment follow-up.

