14.2.2 Mycological Testing

14.2.2.1 Vulvovaginal Candidiasis

Samples for fungal culture will be collected at Screening, EOT (Day 7), TOC (Day 17 [± 3]) and 25-Day FU (25 days after EOT; 32 days after first dose). Additional samples will be obtained, if applicable, at Baseline/Day 1 and at any unscheduled visits. For symptomatic subjects, samples will also be collected at the 35-Day FU visit (35 days after EOT; 42 days after first dose).

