18.4.2.2 Recurrence

Recurrence is defined as Global Response at EOT but re-emergence of the baseline fungal disease during the post treatment follow-up. Re-emergence of the fungal disease is required to be with the same species and involving the same site that was initially identified at Baseline.

Recurrence will be assessed at the 25-Day FU visit (25 days after EOT, 32 days after first dose) for subjects with VVC and at the 6-Week FU (42 days after EOT) for all other subjects as a secondary efficacy endpoint. For CPA subjects, recurrence will also be assessed at Day 180.

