18.4.3 Efficacy Analyses

The primary efficacy endpoint is the percentage of subjects with Global Response (clinical, radiological and mycological) as determined by the DRC at TOC for VVC (Day 17), CMC (EOT or Day 84), CPA and ABPA (EOT or Day 90) (whichever comes first), and at EOT for all other diseases. Results will be presented separately for each disease category along with a 95% confidence interval (CI) for a single binomial proportion in the ITT, Myco-ITT and PP populations where sufficient cases are available. In addition, the number of subjects with a successful response across all disease categories will be summarized as a response rate and 95% CI.

Secondary endpoints will be presented with 95% CIs for the ITT, Myco-ITT and PP populations using the same approach as for the primary endpoint.

The estimated response rates and 95% CIs outlined will also be assessed relative to the external data described in [Section 10.1](#).

The percentage of subjects surviving at the defined time points will be presented for the ITT, Myco-ITT and PP populations. A Kaplan Meier plot will also be produced

summarizing the survival curve over time and the median time to death. A subject without a reported death will be censored at the point of last time the subject was known to be alive.

For primary and overall secondary endpoints, presentations by pathogen will be conducted, if numbers allow.

Data for all subjects will be presented by fungal disease, disease category, reason for enrollment and receipt of combination therapy (Yes/No). If data are missing and the subject has not been deemed a success or failure the outcome will be categorized as unknown/not evaluable.

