	For VVC: TOC (Day 17) (Day 17, 25-Day FU [Day 32], 35-Day FU [Day 42])	For VVC: Global Response = Clinical Success , defined as at least 50% reduction from baseline in total composite score, without use of additional antifungal	For VVC: Global Response (as defined) Clinical Response : 
 
• Clinical Cure, defined as complete resolution of all signs and symptoms (VSS = 0) without use of additional antifungal (Reference FDA guidelines 2016); OR
 
• Resolved VVC infection (VSS < 3)
 
 Mycological Response : 
 
• = mycological eradication of the baseline pathogen OR
 
• Presumed eradication of the baseline pathogen Symptom resolution at FU (clinical cure, resolved infection, clinical success)
 
 Responder outcome (clinical cure and mycological eradication)

Fungal disease	Primary time point (Secondary time points)	Primary Outcome Definition	Secondary Outcome Definitions (disease-specific outcome definitions, if not previously defined) a, e
Disseminated/invasive dimorphic fungi: 
 
• Coccidioidomycosis
 
• Histoplasmosis
 
• Blastomycosis
 
	EOT (EOT, Day 42, Day 84, 6-Week FU)	Global Response = Global Response based on MSG-EORTC outcome response definitions b	Global Response (as defined) Clinical Response (including radiological outcome) and Mycological Response Clinical and Mycological Responses based on MSG-EORTC outcome response definitions b

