### 7.1.1 Primary Analysis

The primary efficacy analysis will be performed at TOC for VVC (Day 17), CMC (EOT or Day 84), CPA (EOT or Day 90) and ABPA (EOT or Day 90) whichever comes first, and at EOT for all other diseases. For CMC, CPA, and ABPA, if Day 84 or Day 90 is the earlier visit and the Global Response is not evaluable or was not done, and the EOT visit has a Global Response, then the EOT information will be used. The number and percentage of subjects with Successful Global Response as determined by the DRC will be presented separately for each fungal disease, disease category, enrollment category, and pathogen along with a 95% confidence interval (CI) for a single binomial proportion in the ITT and PP populations. The Clopper Pearson method will be used for the confidence interval. CI will not be estimated when the subjects in a particular disease, disease category, enrollment category, or pathogen is less than 5. In addition, the overall response will be presented for all disease categories combined.

The following disease categories and fungal diseases will be used for the analysis.

- Acute invasive candidiasis (IC), including candidemia
  - Acute IC with/without candidemia
  - Candidemia only
- Chronic candidiasis
  - Chronic IC
  - Chronic mucocutaneous candidiasis (CMC)
- Mucocutaneous candidiasis
  - OPC (including oropharyngeal, laryngeal)
  - EC
  - VVC
- Disseminated /invasive dimorphic fungi
- Aspergillus syndromes
  - CPA
  - ABPA
  - IPA
- Other emerging fungi

The following pathogens will be used for the analysis.

- Invasive Candidiasis, including candidemia
  - Albicans
  - Auris
  - Glabrata
  - Krusei
  - Parapsilosis
  - Tropicalis

- Other Candida species
- Mucocutaneous Candidiasis (CMC, OPC, EC, VVC)
  - Albicans
  - Auris
  - Glabrata
  - Krusei
  - Parapsilosis
  - Tropicalis
  - Other Candida species
- Dimorphic fungi
  - Coccidioidomycosis
  - Histoplasmosis
  - Blastomycosis
  - Other Dimorphic fungi species
- Aspergillus Syndromes (CPA, ABPA, IPA)
  - Flavus
  - Fumigatus
  - Nidulans
  - Terreus
  - Other Aspergillus species

Invasive Candidiasis will be grouped according to the following sites of infection:

- Pleural/Pulmonary
- Intraabdominal / Pelvic
- Soft tissue/wound
- Endovascular/endocarditis
- Mediastinitis
- Osteomyelitis
- Native joint
- Prosthetic joint
- Urinary tract
- Other

The following enrollment categories (as determined by DRC unless otherwise stated) will be used for the analysis.

- Refractory

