**Mycological Response (Protocol Amendments 2 and 3 aligned with MSG-EORTC outcome response definitions):**

1. Eradication (eradication of the original causative organism cultured or identified by histology/cytology at Baseline)
2. Presumed eradication (missing documentation of the eradication of the original causative organism at Baseline plus resolution of all or some clinical symptoms and physical findings of fungal disease present at Baseline and/or of those that appeared at a subsequent visit)
3. Persistence (persistence of the original causative organism cultured or identified by histology/cytology at Baseline or emergence of a new causative organism)
4. Presumed persistence (missing documentation of the persistence of the original causative organism at Baseline plus no resolution or worsening of any clinical symptoms and physical findings of fungal disease present at Baseline and/or of those that appeared at a subsequent visit)
5. No mycological follow-up results available, for whatever reason (no diagnostic test done at any time point)
6. No mycological evidence at Screening (up to Day 7) (any negative diagnostic test(s) obtained or not done at Baseline [from Screening up to Day 7, inclusive])

Mycological response will be confirmed by the DRC and will include central laboratory results. Reporting of mycological response by PI used different definitions for subjects enrolled under final protocol and subsequent amendments. Complete and partial response were mapped as successful mycological response for subjects under final protocol: Eradication and presumed eradication were mapped as successful mycological response for subjects enrolled under subsequent amendments. The DRC adjudicated mycological responses used the same definition for all subjects as included in the latest amendment.

If relevant mycology findings occur after successful mycological response (proven or presumed eradication), an evaluation will be made as to whether the infection is recurrent (same species as at Baseline) or emergent (different species compared with Baseline). Subjects with recurrent or emergent infection will be classified as mycological failure from the visit onwards where positive cultures were reported, i.e. positive cultures before the FU Visit will be categorized as mycological failure and overall non-successful response on the primary efficacy assessment.

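### Read literally, the rule on positive cultures before the FU visit lets a culture taken after EOT or TOC reverse a primary success, against the plan's own fixed primary time point

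*SAP*

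**What the plan says.** The rule appears in the same words in SAP 7.2.3 and Protocol 18.4.5, both headed as the Investigator's assessment of overall response. It concerns mycology findings that arise after proven or presumed eradication, and it has two halves:

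- First half: "Subjects with recurrent or emergent infection will be classified as mycological failure from the visit onwards where positive cultures were reported".
- Second half, offered as an explanation of the first: "positive cultures before the FU Visit will be categorized as mycological failure and overall non-successful response on the primary efficacy assessment".

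The primary time point is set elsewhere. SAP 7.1.1 has "The primary efficacy analysis will be performed at TOC for VVC (Day 17), CMC (EOT or Day 84), CPA (EOT or Day 90"), with ABPA treated like CPA, the earlier visit taken, and EOT for all other diseases. Protocol 18.4.3 takes the response "as determined by the DRC at TOC for VVC (Day 17), CMC (EOT or Day 84), CPA and ABPA (EOT or Day 90"), again with EOT for the rest. Protocol 9.1 and SAP 7 agree. SAP 7.1.1 adds one substitution: where the Day 84 or Day 90 response is missing or not evaluable, the EOT response is used.

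Recurrence is a separate, DRC-determined secondary endpoint. Protocol 18.4.2.2 states: "Recurrence is defined as Global Response at EOT but re-emergence of the baseline fungal disease during the post treatment follow-up". Protocol 7.2 gives the VVC variant: "Recurrence is defined as Global Response at EOT (TOC for VVC) but re-emergence of the baseline fungal disease". Both require the same species and the same site.

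For VVC, the primary outcome in SAP Table 5 is clinical success, "defined as at least 50% reduction from baseline in total composite score, without use of additional antifungal". For ABPA it combines cough and dyspnea, chest imaging and total IgE.

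**The concern.** The FU visit follows the primary time point in every disease. A rule that lets any positive culture before FU decide the primary result therefore reaches past the moment at which that result is supposed to be settled. The same subject could be a primary success under SAP 7.1.1 and a primary non-success under SAP 7.2.3.

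At stake is what the primary rate means: response at EOT or TOC, or response sustained until close to FU. Protocol 18.4.3 assesses the rates against external data, and SAP 7.1.1 reports them in small disease, enrollment and pathogen groups, so the two meanings should not be mixed. Literal use of the rule can only lower the primary rate. Where recurrence depends on a Global Response at the same visit, it can also remove subjects from the recurrence count.

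**Working it through.** The plan has no figure to reproduce here. The check compares the rules, works out the calendar, and then shows the effect per subject.

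**1. Interval in which the rule can act backwards**

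- Diseases assessed at EOT: FU is 42 ± 7 days after EOT, so 35 to 49 days.
- VVC: Day 32 − Day 17 = 15 days, or 12 to 18 with the ± 3-day TOC window.
- CMC treated to Day 180: FU at 180 + 42 = Day 222 (the study length in Protocol 10.3), and 222 − 84 = 138 days.
- CPA treated to Day 180: 222 − 90 = 132 days.
- CMC or CPA where EOT is itself the TOC: 42 days.

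The rule does not say which FU visit it means. VVC has a 25-Day and a 35-Day FU, and ABPA has three FU visits.

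**2. Whether cultures can fall in that interval**

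They can. Protocol Table 10 schedules CPA mycology at Day 90, Day 180 and EOT, and CMC mycology at Day 84 and EOT. Protocol 14.2.2.3 asks for cultures when relapse is suspected during follow-up. For EOT diseases, Table 10 also has a Day 42 sample (window Days 35 to 49). With EOT on day E, the EOT visit window ends at E + 3 and the FU window opens at E + 35. The whole Day 42 window lies between them when E + 3 < 35 and 49 < E + 35, that is, for E from 15 to 31. At the mean treatment of about 37 days in the preliminary review of 20 subjects (Protocol 7.1), Days 41 to 49 qualify: 9 of the 15 window days.

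**3. The rules side by side**

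- *EOT disease: success at EOT, then the same species at the same site before FU.* SAP 7.1.1: primary success. First half of the rule: failure from that later visit. Protocol 18.4.2.2: a candidate for recurrence, which presupposes success at EOT. Second half of the rule: primary non-success, which removes that precondition.
- *Different species after the primary time point, or an on-treatment positive in CMC or CPA between TOC and EOT.* Neither is recurrence. The conflict is only with the primary time point and with the first half of the rule.
- *VVC.* Cultures are listed as follows: "Samples for fungal culture will be collected at Screening, EOT (Day 7), TOC (Day 17" ± 3 days), and again at the 25-Day FU. Eradication at Day 7, a positive culture at Day 17 and a score reduced by at least half is success under Table 5 and non-success under the rule. This conflict occurs at the primary time point, so it is one of definition rather than timing.
- *ABPA.* The definition conflicts in the same way, but Table 10 schedules no ABPA mycology, and mycological response there is a fall in IgE.

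Protocol 18.3 supports a frozen primary result. For CMC, CPA and ABPA subjects still on treatment at database lock, data up to TOC enter the analyses and later data go to a supplementary analysis.

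**4. Effect per reclassified subject**

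- Overall: 1/220 = 0.45 points (1/242 = 0.41 with the 10% allowance).
- Category of 20: 1/20 = 5 points. Category of 5, the smallest given a confidence interval: 1/5 = 20 points.
- Illustration with the 11/20 of the preliminary review (Clopper-Pearson 95% CI): 55.0% (31.5 to 76.9). One subject reclassified: 10/20 = 50.0% (27.2 to 72.8). Two: 9/20 = 45.0% (23.1 to 68.5).
- Illustration at N = 220, assuming 55% success: 121/220 = 55.0% (48.2 to 61.7). If 5% of successes (6) were reclassified: 115/220 = 52.3% (45.5 to 59.0). If 20% (24): 97/220 = 44.1% (37.4 to 50.9). The 5% and 20% are assumptions; the documents give no such figure.

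**The case against.** The best defence is that the rule sits in the Investigator section, while the primary endpoint belongs to the DRC. Protocol 18.4.2 and SAP 7 send the DRC's criteria to its Charter, and SAP 7.1.1 tabulates the adjudicated result without any culture-date algorithm. This stands in part. It weakens any fear that programmers would derive different rates, and it makes the recurrence conflict conditional on the DRC using the rule. It does not dispose of the point: the sentence names the primary efficacy assessment, which only the DRC determines, and SAP 7.2.3 says that the DRC confirms mycological response.

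A second defence is that the explanatory half merely restates the forward-running half, so that only cultures up to EOT or TOC were meant. That reading is coherent, but it is not written, and it does not remove the VVC conflict at Day 17. Partial response and the step-down definition in SAP Table 6 already require no new positive cultures, but they do not move the assessment beyond EOT.

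Third, opportunities are limited. Non-bloodstream follow-up cultures are not mandatory, Candida follow-up cultures are largely taken as clinically indicated, and the VVC Day 7 contact may be by phone in asymptomatic subjects. All of this stands, and it is why no count can be given. The phone contact does not exclude the VVC case, because presumed eradication also counts as mycological success there.

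Finally, counting early relapse as failure is a legitimate conservative choice. It would, however, be a different endpoint from the one the plan states repeatedly.

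**Conclusion.** The inconsistency is real and should be fixed. Followed literally, the rule gives a primary classification that contradicts the stated time point and its own first half. For same-species, same-site positives after EOT (TOC for VVC), it also contradicts the recurrence definition if it binds the DRC. The VVC and ABPA definitions conflict with it whatever the timing; for ABPA this is largely hypothetical.

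A reader might infer that the DRC's primary results have already been lowered in this way. The documents do not support that. SAP 1.1 describes DRC adjudication in the past tense but does not say that this rule was applied to Global Response. A reader might also take the illustrative rates as an expected bias. They are not: the number of affected subjects is unknown, and only the shift per subject is firm. The study is exploratory, with no formal sample-size calculation, so what is affected is the meaning of the reported rates, chiefly in small categories.

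**What to change.** In SAP 7.2.3 and Protocol 18.4.5:

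- Replace the reference to the FU visit with: *up to and including the primary time point used for that subject (EOT or TOC, including the EOT substitution in SAP 7.1.1)*.
- State that later positives leave the primary Global Response unchanged. They count as failure at later visits, and as recurrence or emergent infection where those definitions are met.
- State that culture results do not alter the VVC and ABPA primary definitions. The new time limit alone would still let a culture override them.
- State whether the DRC applied the rule. List subjects with a positive culture between the primary time point and FU, and re-read those cases only if it did.

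If response sustained to FU is of interest, report it as a named supplementary analysis. Later loss of response already shows in the secondary time points and the recurrence endpoint.

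Cost: one sentence and one clause in each document, one statement about the DRC and one listing, plus the administrative work of changing protocol text. No new data are needed. Re-adjudication arises only if the DRC used the rule.

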## 8. Safety

The safety analyses will be performed on all subjects in the safety population. Analyses will be based on adverse events, vital signs, clinical laboratory assessments, and physical examination findings. Safety analyses in general will be descriptive and will be presented in tabular format with the appropriate summary statistics.

Individual subject listings will be provided to support the tables.

### 8.1 Adverse Events

All AE summaries will be restricted to treatment-emergent AEs (TEAEs) only. A TEAE is defined as any event not present before exposure to study drug or any event already present that worsens in either intensity or frequency after exposure to study drug.

For the purpose of inclusion in TEAE tables, incomplete AE start and end dates will be imputed as follows:

Missing onset dates (where UK and UNK indicate unknown or missing day and month respectively):

- UK-MMM-YYYY: If the month and year are different from the month and year of the date of first dose, assume 01-MMM-YYYY. If the month and year are the same as the month and year for the date of first dose, and the end date (after any imputation) is on or after the date of first dose, then assume the date of first dose. If the month and year are the same as the date of first dose, and the end date (after any imputation) is prior to the date of first dose, then assume the end date for the start date.
- DD-UNK-YYYY/UK-UNK-YYYY: If the year is different from the year of the date of first dose, assume 01-JAN-YYYY of the collected year. If the year is the same as the date of first dose year, and the end date (after any imputation) is on or after the date of first dose, then assume the date of first dose. If the year is the same as the date of first dose, and the end date (after any imputation) is prior to the date of first dose, then assume the end date for the start date.

Missing end dates (where UK and UNK indicate unknown or missing day and month respectively):

- UK-MMM-YYYY: Assume the last day of the month;
- DD-UNK-YYYY/UK-UNK-YYYY: Assume 31-DEC-YYYY.

All adverse events will be classified by SOC and PT according to the Medical Dictionary for Regulatory Activities (MedDRA, March 2023 Version 26.0). An overview summary of the number and percentage of subjects with any TEAE, serious TEAE, treatment-related TEAE,

treatment-related serious TEAE, TEAE leading to study treatment discontinuation, TEAE leading to study discontinuation, and AE leading to death will be provided.

All AEs will be presented in a listing.

